4.7. Procedures

Subjects included in the study will undergo the following investigations:

1. Detailed personal medical history (age of participant, ethnicity, smoking, diet, etc.) and family history of eye diseases (15 minutes)
2. Retinal structure, visual and behavioural test series (45 minutes)

- Refractive error
- Distance Visual Acuity (DVA)
- SKILL card
- Contrast sensitivity
- Pupillometry
- Confrontational visual fields
- Direct ophthalmoscopy
- Psychomotor capability

3. System performance
 - Dark-adaptometry testing (45 minutes)
4. System usability (15 minutes)
 - Ad hoc pen-and-paper questionnaire to assess comfort and ease of use of the novel dark-adaptometer

Subjects will have investigations (1-2) during the screening phase.

Retinal structure, visual and behavioural tests (3) will be carried out once at baseline.

Follow-up visits include dark-adaptometry testing (4), which will be carried out 3 times over 3 weeks. A minimum 1-day window is required after each testing phase.

System usability (4) will be assessed twice, respectively upon completion of the first and the last dark-adaptometry testing visit.

[figure not shown]

Figure 2. Flow-chart of the study design and steps

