The absolute threshold will be the last measured threshold and recorded as the dimmest light that the subject can detect when the rod sensitivity of the study eye is maximum. In a healthy adult, the absolute threshold is typically equal to a logarithmic light intensity around 10^{-6} cd/m^2 at a time of around 30 minutes from the start of the test.

The examiner will monitor in real-time the testing results on a laptop, which is USB-connected to the frame of the goggles from the same side of the study eye. A best fit of collected threshold measurements will be calculated; from this fit, a biphasic curve is expected to be observed.

The rod-cone break will be identified as the point of phase-change in the calculated curve, which coincides with the point when rods become more sensitive than cones. In a healthy adult, the rod-cone break is typically equal to a logarithmic light intensity around 10^{-3} cd/m^2 at a time of around 7 minutes from the start of the test.

The slope of the rod-mediated response will be also calculated from the best fit of the collected threshold measurements. Particularly, the slope of the (second) S2 and (third) S3 rod-mediated component of recovery will be identified: these coincide with a long section of near linear slope following the initial rapid nonlinear increase in rod sensitivity.

An ad hoc pen-and-paper system usability questionnaire will be presented to participants twice upon completion of the first and the last dark-adaptometry testing visit. Participants will rate comfort and ease of use of the system on a scale of 1-10 through questions targeting hardware and software implementation as well as testing duration and expectations.

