Cone- and rod-mediated parameters were compared to previous literature on human dark adaptation to evaluate the performance of the developed dark adaptometer. Clinical data reported in [6] were particularly taken into consideration since a similar DA protocol was used by Jackson et al. to assess dark adaptation changes with age and as a function of decade. In addition, trial outcomes of interest were the test-retest and usability score results and variability obtained from participants after one or multiple DA visits.

Repeatability coefficient (RC) and within-case coefficient of variance (wCV) were calculated starting from the within-subject variance for each trial participant who completed at least 2 DA visits in order to assess variation in repeat measurements on the same patient. Intra-class correlation coefficient (ICC) – 2-way mixed-effects, absolute agreement, average measurement – was calculated for both

Group 1 and Group 2 through SPSS® Statistics V22.0 (IBM, Armonk, USA) to obtain the proportion of total variation in measurements by between-patient differences.

A pen-and-paper questionnaire as in Appendix 1-a was presented to participants twice on completion of the first and the third DA appointment. Seventeen questions targeting hardware and software implementation as well as personal feedback on the duration of the DA test were asked to rate comfort and ease of use of the developed system.

- [1] Alpern M. et al. Rhodopsin kinetics in the human eye. *Journal of Physiology*, 217 (1971), pp. 447-471.
- [2] W.A.H. Rushton, D.S. Powell. The rhodopsin content and the visual threshold of human rods. *Vision Research*, 12 (1972), pp. 1073–1081.
- [4] T.D. Lamb. Spontaneous quantal events induced in toad rods by pigment bleaching. *Nature*, 287 (5780) (1980), pp. 349-351.
- [5] T.D. Lamb. The involvement of rod photoreceptors in dark adaptation. *Vision Research*, 21 (12) (1981), pp. 1773-1782.

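### The SAP specifies an average-measures ICC but describes the single-measures ICC, so the reported figure would overstate the reliability of one test

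*SAP*

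**What the plan says.** The SAP's paragraph on repeatability plans three statistics. The repeatability coefficient (RC) and the within-case coefficient of variance (wCV) come from the within-subject variance "for each trial participant who completed at least 2 DA visits", and their purpose is given as "in order to assess variation in repeat measurements on the same patient". The third is an ICC for each age group, specified as "2-way mixed-effects, absolute agreement, average measurement" and calculated "to obtain the proportion of total variation in measurements by between-patient differences".

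The number of repeats comes from two places. Protocol section 4.7 plans dark-adaptometry "which will be carried out 3 times over 3 weeks", and the SAP's questionnaire paragraph has the form completed "on completion of the first and the third DA appointment".

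Protocol section 4.8 defines both primary outcomes from a single test session: "The absolute threshold will be the last measured threshold", and "The rod-cone break will be identified as the point of phase-change in the calculated curve". Section 4.4 plans 10 participants in each group. Research question III in Protocol section 3 asks whether the system's test results are repeatable.

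**The concern.** The form of ICC and the meaning attached to it do not match. A reader who relies on the SAP's description would take the reported value as the patient share of the variation in individual tests. The statistic named would instead give that share for an average over visits, in which visit-to-visit error has been partly averaged out.

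At stake is the answer to question III. The device's reliability in one sitting would be credited with the higher reliability of a mean of three sittings. The ICC would also look inconsistent with the RC reported beside it, and nothing in the SAP would explain why.

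**Working it through.** **What the description refers to.** The sentence just before the ICC in the SAP uses the word measurements for the individual repeats on one patient. Protocol section 4.8 takes the absolute threshold from the last threshold of a test and the rod-cone break from that test's fitted curve. Neither document defines a participant's result as a mean over visits. The natural reading is therefore variation among single tests.

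**Definitions.** Let Vb, Vc and Ve be the between-patient, between-visit and residual variances.

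- Single measures, absolute agreement: r = Vb / (Vb + Vc + Ve). This is the quantity that the SAP describes.
- Average measures, absolute agreement: A = Vb / (Vb + (Vc + Ve)/k). This is the quantity that the SAP specifies.
- Hence A = k·r / (1 + (k − 1)·r), and in reverse r = A / (k − (k − 1)·A).

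**The link is exact for the estimates too.** With n participants and mean squares MSR (patients), MSC (visits) and MSE (residual):

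- r = (MSR − MSE) / (MSR + (k − 1)·MSE + k·(MSC − MSE)/n)
- A = (MSR − MSE) / (MSR + (MSC − MSE)/n)

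Putting the first into k·r / (1 + (k − 1)·r) gives the second, whether or not there is a visit effect.

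**Inputs.** k = 3 from the planned visits. The documents give no ICC value or variance component, so there is no stated figure to reproduce and r is assumed over a range.

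| Assumed r | A at k = 3 | Gap | A at k = 2 |
|---|---|---|---|
| 0.30 | 0.90/1.60 = 0.56 | 0.26 | 0.46 |
| 0.50 | 1.50/2.00 = 0.75 | 0.25 | 0.67 |
| 0.70 | 2.10/2.40 = 0.88 | 0.18 | 0.82 |
| 0.80 | 2.40/2.60 = 0.92 | 0.12 | 0.89 |
| 0.90 | 2.70/2.80 = 0.96 | 0.06 | 0.95 |

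The k = 2 column applies only if the ICC were run on two visits.

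**Largest gap at k = 3.** The slope of 3r/(1 + 2r) is 3/(1 + 2r)². Setting this to 1 gives r = (√3 − 1)/2 = 0.366, where A = 0.634 and the gap is 0.268.

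**What a reader would infer.** At r = 0.30, 0.50 and 0.70, the part of single-test variation that is not due to patients is 70%, 50% and 30%. Read through the SAP's description, the reported values imply 44%, 25% and 12.5%.

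**Comparison with the RC.** With no visit effect (assumed) and between-patient SD sb, the within-patient SD is sw = sb·√((1 − r)/r), which is 1.528, 1.000 and 0.655 sb at the same three values. The RC is 1.96·√2·sw = 4.23, 2.77 and 1.81 sb. An ICC of 0.75 could therefore stand next to an RC of 2.8 between-patient SDs.

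**At the planned group size.** In 20,000 simulated tables of 10 participants by 3 visits for each assumed r, with normal data and no visit effect, the median single and average estimates were 0.28 and 0.54 at r = 0.30, 0.49 and 0.74 at r = 0.50, and 0.69 and 0.87 at r = 0.70. This shows the sizes expected with 10 people. The mismatch itself follows from the algebra.

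**The case against.** The SAP states the model, type and unit of the ICC openly and never calls it the reliability of one test, so a careful reader can convert it exactly once k is known. The ICC is not among the listed primary or secondary outcomes, and no threshold, decision rule or sample size depends on it. The RC and wCV both come from the within-subject variance, so single-test figures would already be in front of the reader. If the device is highly repeatable, the gap is small: 0.12 at r = 0.80 and 0.06 at r = 0.90. The documents also do not rule out analysing visit means, and k = 3 is inferred.

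Most of this stands, and it limits the importance of the point. It does not remove the mismatch. The open label is contradicted by the SAP's own account of what the number means, and k is not stated beside it. Not ruling out visit means is not the same as defining results that way, and the surrounding text is about single tests. On k, the plan is for three visits; the remaining gap is that participants with two visits enter the RC and wCV but their place in the ICC is not stated. With k = 2 the gap is smaller but has the same direction.

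**Conclusion.** The concern holds. As written, the specified ICC does not deliver the quantity that the SAP says it delivers, and it is the higher of the two whenever the single-test ICC lies strictly between 0 and 1. With three visits the overstatement is at most 0.27. It is about 0.25 at a single-test ICC of 0.50 and falls to 0.06 at 0.90. These sizes rest on k = 3 and on assumed single-test ICCs; the direction does not depend on which value in that range is assumed. The point should be corrected because it bears on question III, but it does not undermine the design, the primary outcomes or the planned RC.

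**What to change.** Make the single-measures, absolute-agreement ICC the reported figure for each group, with a 95% confidence interval, since each group has only 10 participants. This matches the description already in the SAP. If the average-measures form is kept, show it as secondary, call it the reliability of a k-visit mean, and state k. Say how participants with only two visits enter the ICC. Keep the RC and wCV as planned.

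The cost is small: the single-measures value comes from the same data and the same mean squares. Because the SAP is written in the past tense, the analysis may already have been run; in that case the ICC values need re-reporting as well as rewording. The only downside is a lower reported ICC.
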